8.1.12 Return and Retention of Study Drug

The clinical study team will be responsible for keeping accurate records of the clinical supplies received from BMS or designee, the amount dispensed to and not used by the subjects and the amount remaining at the conclusion of the trial. Upon completion or termination of the study, all unused and/or partially used investigational product will be destroyed at the site per institutional policy. It is the Investigator's responsibility to arrange for disposal of all empty containers, provided that procedures for proper disposal have been established according to applicable federal, state, local and institutional guidelines and procedures, and provided that appropriate records of disposal are kept. Inform BMS on all drug destructions pertaining to both nivolumab and ipilimumab.

Table 8.1 – Nivolumab Product Information

Product Description and Dosage Form	Potency	Primary Packaging (Volume)/Label Type	Secondary Packaging (Qty) /Label Type	Appearance	Storage Conditions (per label)
Nivolumab BMS-936558-01 Solution for Injection	100 mg (10 mg/mL)	10 mL vial	5 vials per carton/ Open-label	Clear to opalescent colorless to pale yellow liquid. May contain particles	2 to 8°C. Protect from light and freezing

8.2 Ipilimumab

8.2.1 Other names

MDX-CTLA-4, MDX-010, Yervoy

8.2.2 Classification and type agent

Human IgG1 Kappa anti-CTLA-4monoclonal antibody

8.2.3 Mode of action

Ipilimumab acts as an immunomodulator by blocking the interaction between of the CTLA-4 receptor and its ligands CD80/CD86. CTLA-4 has been shown augment T-cell proliferation and activation.

8.2.4 Storage and stability

Ipilimumab injection is a sterile, nonpyrogenic, clear to slightly opalescent, colorless to pale yellow solution, single-use, preservative-free, isotonic aqueous solution that may contain particles. It is formulated at a concentration of 5 mg/mL ipilimumab in TRIS hydrochloride

NU Study Number: NU 16N03
BMS Study Number: CA 209-802

(also known as 2-amino-2-hydroxymethyl-1,3-propanediol hydrochloride), sodium chloride, mannitol, pentetic acid (also known as diethylenetriaminepentaacetic acid or DTPA), polysorbate 80, and water at pH 7.0. Sodium hydroxide and/or hydrochloric acid may be used to adjust the pH of the solution.

Ipilimumab Injection 50 mg/10 mL (5 mg/mL) is packaged in a 10-cc Type I flint tubing glass vials, stoppered with 20-mm gray butyl rubber stoppers, and sealed with 20-mm aluminum flip-off seals. Each vial includes a 0.7-mL overfill for vial, needle, and syringe (VNS) holdup

Ipilimumab injection, 50 mg/10 mL (5 mg/mL), must be stored refrigerated (2°C to 8°C) and protected from light. Ipilimumab injection must not be frozen. Partially used vials or empty vials of ipilimumab injection should be discarded at the site according to appropriate drug disposal procedures.

Ipilimumab injection may be stored undiluted (5 mg/mL) or following dilution in 0.9% sodium chloride injection or 5% dextrose injection in PVC, non-PVC/non-DEHP, or glass containers for up to 24 hours at 2°C to 8°C or room temperature/room light.

Recommended safety measures for preparation and handling include protective clothing, gloves, and safety cabinets.

8.2.5 Protocol dose specifics

1mg/Kg

8.2.6 Preparation

Ipilimumab injection, 50 mg/10 mL (5 mg/mL), can be used for intravenous (IV) administration without dilution after transferring to a polyvinyl chloride (PVC), non-PVC/non-di(2-ethylhexyl)phthalate (DEHP), or glass container and is stable for 24 hours at 2°C to 8°C or room temperature/room light. Ipilimumab injection may be diluted in 0.9% sodium chloride injection or 5% dextrose injection to concentrations between 1 mg/mL and 4 mg/mL and stored in PVC, non-PVC/non-DEHP, or glass containers for up to 24 hours at 2°C to 8°C or room temperature/room light. The product may be infused using a volumetric pump at the protocol-specific dose(s) and rate(s) through a PVC IV solution infusion set with an in-line, sterile, nonpyrogenic, low protein binding filter (pore size of 0.2 µm to 1.2 µm). Ipilimumab injection must not be administered as an IV push or bolus injection. Care must be taken to assure sterility of the prepared solutions since the drug product does not contain any antimicrobial preservatives or bacteriostatic agents.

8.2.7 Route of administration for this study

Intravenous infusion. Do not administer using IV push or bolus. Administer through a volumetric pump with a 0.2 to 1.2 micron in-line filter (non- pyrogenic and low-protein binding). At the end of the infusion, flush the line with a sufficient quantity of approved diluents.

8.2.8 Incompatibilities

No formal pharmacokinetic drug interaction studies have been conducted with ipilimumab

8.2.9 Availability & Supply

The supply for this study will be investigational – not commercially available. Supply will be provided by BMS free of charge. Ipilimumab will be supplied as 50mg /vial (5mg/mL) packaged in cartons of 6 vials. Drug is protocol specific, but not patient specific.

NU Study Number: NU 16N03
BMS Study Number: CA 209-802

Drug can be ordered using the Drug Request Form provided by BMS. The form is provided as a separate document and should be submitted electronically at least 7 business days for initial order and at least 14 days for re-supply before the expected delivery date. Contact and submission details can be found directly on the Drug Request Form.

Deliveries will be made Tuesday through Friday.

Starting January 2023, Ipilimumab will be supplied in 50mg vials. Each carton will contain 6 x 50mg vials.

Ipilimumab product supply			
Container description	Type: Single-use vials of 50 mg/10 mL	Material: clear glass	Size: 10 mL vials
Active ingredient content	Mass/Weight: 50 mg	Volume: 10 mL	Concentration: 5 mg/mL

Table 8.2 – Ipilimumab Product Information

Product Description and Dosage Form	Potency	Primary Packaging (Volume)/Label Type	Secondary Packaging (Qty) /Label Type	Appearance	Storage Conditions (per label)
Ipilimumab Solution for Injection	50 mg (5 mg/mL)	10 mL vial	6 vials per carton/Open-label	Clear, colorless to pale yellow liquid. May contain particles	2 to 8°C. Protect from light and freezing.

8.2.10 Side effects

Immune-related adverse events have been associated with ipilimumab when administered intravenously.

Since its first approval for advanced melanoma in the US on 25-Mar-2011, followed by European Medicines Agency approval in the EU on 13-Jul-2011, ipilimumab has been approved for market use in 47 countries worldwide. Based on information published in the ipilimumab Periodic Benefit-risk Evaluation Report (PBRER) #5, cumulatively through 24-Mar-2015 (the cutoff date for the last PBRER), approximately 30,540 patients have been exposed to ipilimumab through marketed drug worldwide (excluding investigator-sponsored trials/research exposure). In addition, 5,877 subjects have been cumulatively exposed to ipilimumab through clinical trials, and 10,486 patients have been exposed to ipilimumab through EAPs. During the reporting period of PBRER #5, 13 clinical trials (including EAPs, CA184045 and CA184089) met the inclusion criteria as ongoing studies, and 1 clinical trial (Study CA184202, Phase 1 to 3) in melanoma was completed. During that reporting period, the Company Core Data Sheet was updated once, on 21-Jan-2015. One new safety signal was identified: drug reaction with eosinophilia and systemic symptoms. For toxic epidermal necrolysis, a known, labeled AE, a cautionary note was added for the specific context when ipilimumab treatment is considered for a patient who has previously experienced a severe or life-threatening skin adverse reaction on a prior cancer immune-stimulatory therapy.

Based on package insert below are safety data from 131 patients with metastatic melanoma who received ipilimumab as monotherapy in a phase 3 trial.

Very Frequent – Expected to occur in more than 20% of people (more than 20 out of 100 people): Fatigue (42%), Pruritus (24.4%), Decreased appetite (26.7%) Diarrhea (32.8%), Nausea (35.1%), Constipation (20.6%), Vomiting (23.7%),

Frequent - Expected to occur in 10% to 20% of people (10 to 20 out of 100 people): Abdominal pain (15.3%), pyrexia (12.2%), headache (14.5%), Cough (16%), dyspnea (14.5%), anemia (11.5%), rash (19.1)

Not Frequent – Expected to occur in less than 10% of people (less than 10 out of 100 people): vitiligo, colitis, hypothyroidism, hypopituitarism and adrenal insufficiency, increased aspartate aminotransferase and alanine aminotransferase

Deaths thought to be related to ipilimumab when given alone were reported in approximately 3 % of subjects treated (approximately 4 out 131 people).

For the most recent safety update, please refer to the current Investigator's Brochure or Study Agent Prescribing Information.

8.2.11 Safety and monitoring plan

All participants will be carefully followed for safety. Participants are seen by their study team before each dose of ipilimumab (every 2 weeks). Safety evaluations at this time include a physical exam, vital signs, performance status assessment, and safety laboratory tests. The study team will continuously monitor participants for treatment side effects. Participants are instructed to inform their study doctor right away if they notice or feel anything different so the study doctor can check for side effects. The study doctor may be able to provide treatment for side

NU Study Number: NU 16N03
BMS Study Number: CA 209-802

effects. The study doctor may temporarily hold the study drug to reduce side effects. The study doctor will permanently stop the study drug if side effects are too severe and/or long lasting. All participants will be followed for side effects for 30 days from their last dose of ipilimumab. Participants with ongoing side effects will continue to be followed until resolution or stabilization of the side effects. Because it is not known if ipilimumab will be effective against anal cancer, to enrollment will stop after 12 participants are treated with ipilimumab if none of them have their tumors shrink. Study team conferences will be held monthly or more frequently if needed.

8.2.12 Return and Retention of Study Drug

The clinical study team will be responsible for keeping accurate records of the clinical supplies received from BMS or designee, the amount dispensed to and not used by the subjects and the amount remaining at the conclusion of the trial.

Upon completion or termination of the study, all unused and/or partially used investigational product will be destroyed at the site per institutional policy. It is the Investigator's responsibility to arrange for disposal of all empty containers, provided that procedures for proper disposal have been established according to applicable federal, state, local and institutional guidelines and procedures, and provided that appropriate records of disposal are kept. Inform BMS on all drug destructions pertaining to both nivolumab and ipilimumab.

Container description	Type: Single-use vials of 50 mg/10 mL	Material: clear glass	Size: 10 mL vials
Active ingredient content	Mass/Weight: 50 mg	Volume: 10 mL	Concentration: 5 mg/mL

9.0 CORRELATIVES/SPECIAL STUDIES

Archival tumor samples, when available, and any tissue that may feasibly be collected from SOC biopsies throughout the study, may be evaluated for the immunosuppressive biomarker PD-L1 protein on tumor cells and the expression level and localization of other markers of inflammatory/immune signature that may include but not be limited to PD-1, OX40, CD73, CD39, T cell immunoglobulin and mucin domain containing protein 3 (TIM3), GITRL, CTLA-4, CD3, CD4, CD8, protein tyrosine phosphatase receptor type C (CD45RO), forkhead box P3 (FOXP3), and granzyme by immunohistochemistry analysis and/or flow cytometry. Comprehensive genomic profiling of the tumor samples will also be performed.

A baseline whole blood sample and serum sample will also be collected for future biomarker analysis that may include tumor and immune cell, poreosome, and exosome analysis at partnering laboratories. Collection and processing instructions are available in a separate lab manual, available on the NOTIS protocol page.

Repeated blood samples will be collected at the time of disease progression and partial or complete response (\pm 2 weeks of confirmation). Details on sample collection, shipping, and processing are available in a separate lab manual.

9.1 Specimen Banking

Patient samples collected for this study will be retained at Robert H Lurie Cancer Center of Northwestern University Pathology Core Facility. Specimens will be stored indefinitely or until they are used up. If future use is denied or withdrawn by the patient, best efforts will be made to stop any additional studies and to destroy the specimens.

The PI will be responsible for reviewing and approving requests for clinical specimen from potential research collaborators outside of Northwestern University. Collaborators will be required to complete an agreement (a Material Transfer Agreement or recharge agreement) that states specimens will only be released for use in disclosed research. Any data obtained from the use of clinical specimen will be the property of Northwestern University for publication and any licensing agreement will be strictly adhered to.

The following information obtained from the subject's medical record may be provided to research collaborators when specimens are made available:

- Diagnosis
- Collection time in relation to study treatment
- Clinical outcome – if available
- Demographic data

10.0 STATISTICAL CONSIDERATIONS

10.1 Study Design/Study Endpoints

This is a single arm open label phase II clinical trial which will assess the anti-tumor efficacy of nivolumab in combination with ipilimumab in ACC. As these two monoclonal anti-bodies already have been studied and approved as monotherapy or combination in other histological tumor types we believe that a phase II study is appropriate for development of these drugs in metastatic/recurrent adenoid cystic carcinoma (ACC). The non-adenoid cystic carcinomas (non-ACC) of major or minor salivary glands are for exploratory purposes for signal finding and will not be included in our statistical plan.

10.1.1 Primary:

To assess the median progression-free survival (PFS) as well as PFS at 6 and 12 months [defined as the absence of death and of progression of disease] in patients with metastatic/recurrent and progressive ACC. The Response Evaluation Criteria in Solid Tumors (RECIST 1.1) criteria will be used for objective tumor response assessment

10.1.2 Secondary:

- (1) To assess the efficacy of nivolumab and ipilimumab according to response rate (RR), disease control rate (DCR; CR, PR, and SD at 24 weeks), overall survival (OS) and progression free survival (PFS) in the above population using RECIST criteria.
- (2) To assess the efficacy of nivolumab and ipilimumab according to ORR, DCR, PFS, and OS in the above population using irRECIST criteria.
- (3) To assess the safety and tolerability profile of nivolumab and ipilimumab therapy in the above population using CTCAE version 4.03
- (4) To assess the immune-related biomarkers and their association with treatment response
- (5) Assess activity of nivolumab and ipilimumab in non-ACC malignant salivary gland tumors (MSGTs)

10.1.3 Exploratory endpoints:

- To assess the predictive value of baseline immunosuppressive biomarker PD-L1 protein on tumor cells and the expression level and localization of

NU Study Number: NU 16N03
BMS Study Number: CA 209-802

other markers of inflammatory/immune signature. Correlations between cell free tumor DNA and tumor tissue genomic aberrations with anti-tumor efficacy of nivolumab/ipilimumab combination will be explored.

10.2 Sample Size and Accrual

A Simon two stage optimum Phase II design will be used ⁴⁶. The main outcome is median Progression Free Survival (PFS) as well as PFS at 6 and 12 months. The optimal two-stage design to test the null hypothesis that $P \leq 0.450$ versus the alternative that $P \geq 0.650$ has an expected sample size of 24.70 and a probability of early termination of 0.654. If the drug is actually not effective, there is a 0.048 probability of concluding that it is (the target for this value was 0.050). If the drug is actually effective, there is a 0.196 probability of concluding that it is not (the target for this value was 0.200). After testing the drug on 15 patients in the first stage, ACC accrual will be terminated if 7 or more patients are withdrawn from the study after <24 weeks of treatment for any reason other than withdrawal of consent (this includes toxicity, PD, intolerance etc.) If the trial goes on to the second stage, a total of 43 patients will be studied. If the total number responding (defined as stable disease or better) is less than or equal to 24, the drug is rejected. An exploratory group of 20 patients with MSGTs will be included in the study, in addition to the 43 patients mentioned above. They can be enrolled in any order within the total accrual of 63 patients and will not participate in statistical analysis. A separate safety analysis will take place; if >2 of the first 10 non-ACC patients are withdrawn after <24 weeks of treatment, non-ACC accrual will discontinue.

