Statistical Methodology	
The main outcome is median Progression Free Survival (PFS) as well as PFS at 6 and 12 months. The optimal two-stage design to test the null hypothesis that $P \leq 0.450$ versus the alternative that $P \geq 0.650$ has an expected sample size of 24.70 and a probability of early termination of 0.654. If the drug is actually not effective, there is a 0.048 probability of concluding that it is (the target for this value was 0.050). If the drug is actually effective, there is a 0.196 probability of concluding that it is not (the target for this value was 0.200). After testing the drug on 15 ACC patients in the first stage, ACC accrual will be terminated if 7 or more patients are withdrawn from the study after <24 weeks of treatment for any reason other than withdrawal of consent (this includes PD, toxicity, intolerance etc.). If the trial goes on to the second stage, a total of 43 patients will be studied. If the total number responding (where response is defined as stable disease or better) is less than or equal to 24, the drug is rejected. An additional exploratory group of 20 patients with non-ACC MSGT will be added concurrently with ACC patients for a total samples size of 63 patients. An additional safety analysis will take place for non-ACC patients; if >2 of 10 non-ACC patients are withdrawn after <24 weeks of treatment, accrual of non-ACC patients will discontinue. Response rates and 95% confidence intervals will be calculated using exact binomial probability distributions for discrete outcomes. Progression-free survival and overall survival will be graphically depicted using Kaplan-Meier curves. Adverse events will be summarized descriptively using frequencies and percentages. Statistics will be given on type, severity, frequency and attribution of adverse events. Sample size considerations are described above.

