2.0 OBJECTIVES & ENDPOINTS

2.1 Primary Objective & Endpoint

To assess median progression-free survival (PFS) as well as PFS at 6 and 12 months in patients with recurrent or metastatic adenoid cystic carcinoma (ACC) treated with a combination of nivolumab and ipilimumab.⁴⁴ Patients will have scans every 12 weeks. Efficacy will be evaluated in all patients who receive at least one dose of study treatment and have had their disease re-evaluated.

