6.2 Primary Endpoint

Median progression-free survival (PFS) as well as PFS at 6 and 12 months [defined the absence of death and of progression of disease. The Response Evaluation Criteria in Solid Tumors (RECIST 1.1) criteria will be used for objective tumor response assessment].⁴⁴

- Clinical and radiological assessments will be performed every 12 weeks (± 7 days) while on treatment. All patients who receive at least one dose of nivolumab and have had their disease re-evaluated will be included in the primary analysis of PFS.

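### Median, 6-month and 12-month PFS are jointly primary, but the single planned test is of an undefined proportion P, so the stated error rates belong to none of them

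*Combined protocol and SAP*

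**What the plan says.** The primary aim is worded the same way throughout. Section 2.1: "To assess median progression-free survival (PFS) as well as PFS at 6 and 12 months in patients with recurrent or metastatic adenoid cystic carcinoma". Section 6.2: "Median progression-free survival (PFS) as well as PFS at 6 and 12 months". Section 10.2: "The main outcome is median Progression Free Survival (PFS) as well as PFS at 6 and 12 months". The Study Summary and Section 10.1.1 repeat the trio. None of them ranks the three, divides alpha between them or says which one decides.

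Section 10.2 and the Statistical Methodology row of the Study Summary then give one Simon optimal design for P of at most 0.45 against P of at least 0.65. The design "has an expected sample size of 24.70 and a probability of early termination of 0.654". On error rates, if the drug is ineffective "there is a 0.048 probability of concluding that it is (the target for this value was 0.050"), and if it is effective "there is a 0.196 probability of concluding that it is not (the target for this value was 0.200"). P is given no name and no time point.

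Two counts carry the decision:
- **Stage 1 (15 ACC patients):** accrual stops if 7 or more are withdrawn before 24 weeks of treatment, for reasons other than withdrawal of consent.
- **Final (43 ACC patients):** the drug is rejected if 24 or fewer respond, response being stable disease or better, with no time point.

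For PFS itself, Section 10.3 plans only Kaplan-Meier curves. No null value, threshold or interval is given for median, 6-month or 12-month PFS by name.

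**The concern.** The operating characteristics of a Simon design describe one binary outcome per patient. Here three quantities are called primary, one proportion is tested, and the text never connects them. Median PFS cannot be P without a conversion that the protocol does not give. Six-month and 12-month PFS could each be P, but not with the same null and alternative: 12-month PFS cannot exceed 6-month PFS, and it is lower as soon as one event falls between the two times. That needs no distributional assumption. The outcome actually counted at the end, stable disease or better at no stated time, is a fourth quantity.

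At stake is what the trial can conclude. If more than 24 of 43 patients have stable disease or better, the protocol permits the drug not to be rejected, yet that result supports no stated hypothesis about any primary endpoint. Conversely, a reported median or landmark PFS will have no pre-specified standard to be judged against. In a single-arm trial the pre-specified decision quantity is the main protection against choosing a favourable reading afterwards.

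**Working it through.** **Inputs.** From Section 10.2: null 0.45, alternative 0.65, n1 = 15, N = 43, final cut 24, early-termination probability (PET) 0.654, expected N 24.70, alpha 0.048, beta 0.196 (power 1 − 0.196 = 0.804). The protocol gives no PFS distribution, so exponential PFS is assumed in steps 2 and 3 and varied in step 4.

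**1. Reproduce the design.** With X1 ~ Bin(15, p), X2 ~ Bin(28, p) and stage 1 cut r1:
- PET = P(X1 ≤ r1)
- E[N] = 15 + (1 − PET) × 28
- P(pass) = Σ over x > r1 of P(X1 = x) × P(X2 ≥ 25 − x)

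With r1 = 7 and p = 0.45, PET = 0.6535, E[N] = 15 + 0.3465 × 28 = 24.70 and P(pass) = 0.0481. With p = 0.65, P(pass) = 0.8035. All stated figures are matched. A full search with alpha ≤ 0.05 and beta ≤ 0.20 returns the same design, 7/15 and 24/43.

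The cut of 7 is inferred from the stated PET. Stopping at 7 or more withdrawn, as written, means stopping at 8 or fewer not withdrawn. If success is the complement of withdrawal, that is r1 = 8: PET 0.818, alpha 0.037, power 0.704.

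**2. What 0.45/0.65 means at each landmark.** Under an exponential curve S(12) = S(6)², and the median is t × ln 0.5 / ln S(t).

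| If P is | Median PFS, null / alternative | PFS at the other landmark, null / alternative |
|---|---|---|
| 6-month PFS | 5.2 / 9.7 months | 12-month: 0.20 / 0.42 |
| 12-month PFS | 10.4 / 19.3 months | 6-month: 0.67 / 0.81 |

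A drug exactly at the alternative on 6-month PFS has 12-month PFS of 0.65² = 0.4225, inside the null. A drug exactly at the null on 12-month PFS has 6-month PFS of √0.45 = 0.67, above the alternative.

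**3. Probability of passing.**

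| Drug | Reading of P | r1 = 7 (implied by PET) | r1 = 8 (as written) |
|---|---|---|---|
| 6-month PFS 0.65 | 6-month | 0.80 | 0.70 |
| 6-month PFS 0.65 | 12-month (0.4225) | 0.02 | 0.016 |

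The drug at the null on 12-month PFS passes the 6-month reading with probability 0.87 (r1 = 7).

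**4. Sensitivity to the curve.** Under a Weibull curve with shape k, S(12) = S(6)^(2^k). From S(6) = 0.65, k = 0.7 gives S(12) = 0.50 and k = 1.3 gives 0.35. The probabilities of passing on the 12-month reading (r1 = 7) are 0.14 and 0.001. The size moves; the direction does not.

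**5. A hypothetical any-of-three rule.** Suppose success could be claimed on the 6-month two-stage test, on a 12-month exact test (14 or more of 43 against 0.2025), or on a one-sided 0.05 test of the median. Simulation with n = 43, the exponential null and no censoring gives a family-wise error of 0.085 (sign test for the median) to 0.096 (exponential test). The 12-month and median tests are constructed for this calculation and are not in the protocol.

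**The case against.** The strongest reply is that the plan has one decision rule and its count is labelled: stable disease or better, 24 of 43. The three PFS quantities are to be assessed, and Section 10.3 only plots them. On that view the verdict on the drug cannot change with the choice of PFS summary, because none of them is tested. This stands, and it limits the point. A reader might infer that the same data would yield opposite verdicts depending on the primary chosen; the written rule does not provide for such a choice.

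A reader might also infer that three primaries inflate the 0.048 false-positive probability. No text allows a claim on any of three tests, so the figures in step 5 describe a procedure that the plan does not contain.

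Nor is there much support for reading P as 12-month PFS. Stage 1 uses 24 weeks, and Section 10.1.2 sets disease control at 24 weeks. The 12-month column shows why P must be defined, not what the authors probably meant.

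What the reply does not do is connect the test to a primary endpoint. The labelled count is none of the three named quantities and has no time point. The 24-week window counts withdrawal from treatment, which differs from PFS in both directions. Section 4.4 lets some patients continue treatment after progression, and Section 4.8 keeps imaging patients who stopped for toxicity without progression. If median and 12-month PFS are meant to be descriptive, the protocol should say so; at present its sample-size section calls them the main outcome.

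**Conclusion.** The point holds as a mismatch between endpoint and test. Three PFS quantities are jointly primary, one undefined proportion is tested, and the final decision uses a fourth quantity. The figures 0.048 and 0.804 are correctly computed for the 7/15, 24/43 design but cannot be quoted for any primary endpoint as written.

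That conclusion needs no distributional assumption. The 0.80 against 0.02 contrast illustrates how much the missing definition matters; it rests on an exponential curve and on the stage 1 cut implied by the PET. The documents do not support a claim that the false-positive rate is actually inflated.

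**What to change.** - In the Study Summary and Sections 2.1, 6.2, 10.1.1 and 10.2, name 6-month (24-week) PFS by RECIST 1.1 as the sole primary endpoint, and define P as the proportion of ACC patients alive and progression-free at that time.
- In Section 10.2 and the Study Summary, rewrite the final count to match: the drug is rejected if 24 or fewer of 43 patients are alive and progression-free at 6 months. If this count is left as stable disease or better, renaming the endpoint achieves nothing.
- Move median and 12-month PFS to the secondary endpoints, as Kaplan-Meier estimates with 95% confidence intervals and no success claim.
- Reconcile the stage 1 count with this endpoint. It counts withdrawals before 24 weeks of treatment, and its cut as written does not give the stated PET.
- Record that the choice was made without sight of outcome data. The protocol is at Amendment 8 (October 2022) of an open-label, single-arm trial, so this needs an explicit statement.

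**Cost.** A protocol amendment. The total of 43, the final cut of 24 and the data collected are unchanged, and all three PFS quantities are still estimated. The loss is that no efficacy claim can rest on median or 12-month PFS.
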